10.3.3.2 Test of Clinical Equivalence

The evaluations of clinical equivalence will be performed for the PP population.

For the primary efficacy assessment, the two-sided, 90% confidence interval on the test/reference ratio of the mean percent change from screening/baseline to week 12 in each lesion type will be calculated using Fieller's method and the pooled variance estimate (MSE) obtained from a two-way Analysis of Variance (ANOVA) of the Test and Reference results. The statistical model for the ANOVA will contain terms for treatment and center. If the skewness of the residuals from the ANOVA is outside of -2 to 2, then a nonparametric approach will be used to obtain the confidence intervals. Bioequivalence will be established if the 90% confidence intervals for the ratio of test/reference means, for both inflammatory and non-inflammatory lesion counts, are contained within the interval [0.80, 1.25] using the per protocol (PP) population.

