5. HYPOTHESES TESTING

Hypothesis of Equivalence

A two-sided, 90% confidence intervals on the test/reference ratio for mean percent change from Baseline in the inflammatory and non-inflammatory lesion counts will be constructed using Fieller's method. The estimates of treatment means and standard errors will be obtained from a two-way Analysis of Variance (ANOVA) of the Test and Reference results, using a statistical model containing terms for treatment and center. Non-parametric methods will be considered if the skewness factor for the residuals from the ANOVA model is outside the range -2 to +2.

Bioequivalence will be established if the 90% confidence intervals for the ratios of test/reference means for both the inflammatory and non-inflammatory lesions are contained within the interval [0.80, 1.25].

Hypothesis of Superiority

The null hypothesis to be tested is that there is no difference in the mean percent change (reduction) from baseline in the inflammatory and non-inflammatory lesion counts between the active treatment and the Vehicle treatment. The hypothesis testing will be performed separately for the Test treatment versus the Vehicle treatment and for the Reference treatment versus the Vehicle treatment using ANOVA under assumption of normal error and homogeneity of variance. Only data for the relevant two treatment arms will be included in each ANOVA. Similarly to bioequivalence, non-parametric methods will be considered if the skewness factor for the residuals from the ANOVA model is outside the range -2 to +2.

Superiority will be established if the mean percent change (reduction) from Baseline in both the inflammatory and non-inflammatory lesion count for each active treatment is greater than, and statistically different from ($p < 0.05$, two-sided), that for the Vehicle.

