7.6.2.1 Analysis of clinical equivalence of test and reference treatments

To show the clinical equivalence, estimates of mean percent change from baseline in the inflammatory and non-inflammatory lesion counts will be calculated for the Test and Reference treatment, and then the 90% CI for the mean ratio will be constructed using Fieller's method. Bioequivalence will be established if the 90% confidence intervals for the

ratios of Test/Reference means are contained within the interval [0.80, 1.25] for the PP population for both lesion types (inflammatory and non-inflammatory).

To this end, first an ANOVA model will be fit (separately for each lesion type) with percent change from baseline in lesion count as outcome and treatment, center and treatment-by-center interaction as factors on the data from Test and Reference treatments only (excluding Vehicle subjects). If the treatment-by-center interaction factor is not significant at the 0.05 level, the model will be rerun without the interaction term. Treatment means and standard errors will be estimated from this model. Then Fieller's formula will be applied; covariance between the treatment means will be assumed to be 0. See [Appendix 11.2](#) for complete description of the Fieller's formula.

A non-parametric rank based ANOVA will be considered when the data is highly skewed. The evaluation of skewness, (using SAS[®] PROC UNIVARIATE) will be performed using the residuals from ANOVA and if the skewness statistic is less than -2 or greater than +2, the analysis will be performed on the ranks of the percent change in the inflammatory lesion count values.

Analysis of bioequivalence will be performed on the PP population

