$$g = \frac{t_{r,\alpha}^2 se_r^2}{m_r^2}$$

Here m_t and se_t are mean and standard error estimate for test treatment and m_r and se_r for reference treatment correspondingly obtained from the above model. The degrees of freedom r can be obtained from the model as degrees of freedom for the error term in the overall ANOVA table, $\alpha = 0.05$ (for the 90% confidence interval). The term $t_{r,\alpha}$ can be calculated in SAS as `tinv(α , r)`.

Evaluation of skewness

This evaluation will be performed on the residuals output by the "output" statement in PROC GLM above:

```
proc univariate data=residuals;  
    var residual;  
run;
```

Non-parameteric rank ANOVA

If decision to use the rank ANOVA is taken, the data will be ranked first:

```
proc rank data=<dataset>  
    var <change_from_baseline>;  
    ranks rank;  
run;
```

After that the analysis will proceed using the same SAS code as described above but using rank variable instead of the original change from baseline.

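### When residuals are skewed, the SAP judges equivalence on ranks against [0.80, 1.25], which does not test the ratio of mean percent change or hold the 5% error

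*SAP*

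**What the plan says.** SAP section 7.6.2.1 fits an ANOVA to percent change in the Test and Reference arms and puts the treatment means and standard errors into Fieller's formula. It declares bioequivalence if the 90% intervals for the "ratios of Test/Reference means are contained within the interval [0.80, 1.25] for the PP population for both lesion types". The per-protocol analysis is the definitive one for equivalence.

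For skewed residuals the texts differ in force and detail:

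- Protocol 10.3.3.2: if skewness is outside -2 to 2, "then a nonparametric approach will be used to obtain the confidence intervals". The approach is not named.
- SAP section 5: "Non-parametric methods will be considered if the skewness factor for the residuals from the ANOVA model is outside the range -2 to +2".
- SAP 7.6.2.1: a rank-based ANOVA is first something to be considered. The next sentence says that beyond ±2 "the analysis will be performed on the ranks of the percent change in the inflammatory lesion count values".
- SAP Appendix 11.2: "If decision to use the rank ANOVA is taken, the data will be ranked first", and then "the analysis will proceed using the same SAS code as described above but using rank variable instead of the original change from baseline".

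The material above that instruction in Appendix 11.2 is the PROC GLM step whose LS means and standard errors feed Fieller, the Fieller formula, and the skewness check. Neither document gives a margin for ranks, a Hodges-Lehmann type interval, a bootstrap or a transformation. None of the sentences cited here is redacted.

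**The concern.** The limits 0.80 and 1.25 have a meaning for the ratio of mean percent change: Test keeps at least 80% of the Reference effect. They have no such meaning for a ratio of mean ranks. Adding a constant to every percent change leaves all ranks unchanged, but it changes the ratio of means. A rank ratio therefore cannot tell a 20% loss of effect from a 33% loss.

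If the trigger fires for a lesion type, this interval decides equivalence for that type, and both types must pass. The primary conclusion would then rest on a different quantity, with an error rate set by the spread of the data. The switch is also worded partly as optional, which leaves the definitive equivalence method open.

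**Working it through.** **Inputs.** From the documents: limits [0.80, 1.25]; a 90% interval, so (1 - 0.90)/2 = 0.05 per tail, which matches the α = 0.05 in Appendix 11.2; trigger |skewness| > 2; zero covariance in Fieller. Sample size, means and SDs are redacted (Protocol 10.1.1, SAP 3.2), so those below are assumed.

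**1. What the limits mean on ranks.** With equal arms ranked jointly, and p = P(Test percent change > Reference percent change), the ratio of mean ranks is approximately

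(0.5 + p)/(1.5 - p).

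Setting this to 1.25 gives 2.25p = 1.375, p = 0.611. Setting it to 0.80 gives 1.8p = 0.70, p = 0.389. No mean reduction appears. Reductions are negative changes and ranks ascend, so a worse Test product gives a ratio above 1.

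**2. When the two scales would agree.** For a normal shift δ with common SD σ, p = Φ(δ/(√2σ)). Then p = 0.611 requires δ/σ = 0.399. At a true ratio of 0.80, δ is 0.20 of the Reference mean reduction, so the scales agree only if σ is 0.20/0.399 = 0.50 of that reduction. Larger SDs make the rank rule too lenient and smaller SDs make it too strict.

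**3. Worked case.** 300 lognormal quantiles per arm, log-SD 0.8, spread proportional to remaining lesions (SD 55.2 for Test, 46.0 for Reference). Residual skewness is 2.88, so the trigger fires. Adding 10 or 20 points to every value gives:

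| Mean reduction, Test/Reference | True ratio | Original-scale Fieller 90% CI | Rank ratio (90% CI) |
|---|---|---|---|
| 40/50 | 0.80 | 0.68–0.93, fails | 1.137 (1.05–1.23), passes |
| 30/40 | 0.75 | 0.61–0.91, fails | 1.137 (1.05–1.23), passes |
| 20/30 | 0.67 | 0.49–0.88, fails | 1.137 (1.05–1.23), passes |

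The mean ranks are 319.7 and 281.3, and p is 0.564.

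**4. Error rate of the whole rule at a true ratio of 0.80.** Week-12/baseline ratio lognormal, Reference reduction 50% or 60%, 200 or 500 per arm, ranks used only when triggered. One lesion type: no centres, 2,000 trials per cell. Both types required: other type truly equivalent, correlation 0.5, 10 centres, 1,500 trials per cell.

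| Log-SD | Trigger fires | Passes, one type | Passes, both types required |
|---|---|---|---|
| 0.4 | 1–4% | 5–6% | not tabulated |
| 0.5 | 17–20% | 5–7% | 4–9% |
| 0.6 | 48–61% | 4–27% | 3–34% |
| 0.7 | 77–94% | 7–63% | 7–70% |
| 0.8 | 93–100% | 16–84% | 17–85% |
| 0.9 | 99–100% | 26–91% | 27–91% |

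Original-scale Fieller passed 3–7% throughout for one type. With a stratified bootstrap in triggered trials, the trial-level rate was 1–6%. Gamma data gave 6% at CV 0.6, 8–9% at CV 0.8 and 20–33% at CV 0.95. At log-SD 0.4–0.5 and 60% reduction, the rank interval itself passed 0.1% or less.

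**5. The SAP path including the interaction pre-test.** 10 centres, 300 per arm, 2,000 trials per cell, true ratio 0.80, pass rates given the trigger:

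| Data model | Rank Fieller | Original-scale Fieller | Bootstrap |
|---|---|---|---|
| Reduction 55%, log-SD 0.7 | 31.2% | 5.2% | 4.8% |
| Reduction 55%, log-SD 0.9 | 57.4% | 5.7% | 5.6% |
| Reduction 45%, 4% large worseners | 21.6% | 5.3% | 5.9% |
| Reduction 65%, log-SD 0.7 | 0.9% | 4.9% | 4.3% |
| Reduction 65%, 2% large worseners | 0.2% | 5.4% | 5.3% |

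Without centres, the first model gave 17.8%, 27.4% and 36.5% at 150, 300 and 500 per arm. In that setting a larger sample makes the error worse.

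**The case against.** The branch may never open. At log-SD 0.4 to 0.5 the whole rule passes 5% to 7%, close to original-scale Fieller, and nothing unredacted shows that wider spreads are expected. This stands as a limit on the expected size of the error, but not on the defect: where the plan's own branch opens, the 5% level is not guaranteed.

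The rank-ratio rule is inferred. Appendix 11.2 reuses code, Fieller is given as a formula, and the criterion is never restated for mean ranks. That is fair. Still, the protocol requires an interval in this branch, and no other interval can be built from what is written.

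The switch may be discretionary, so rates that apply ranks whenever triggered are upper bounds where spreads are wide. This also stands, but choosing the definitive method after seeing the residuals is a weakness in itself.

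The worked case depends on Test having the larger spread. With equal SDs of 46.0, the rank ratio is 1.244 (1.15–1.35) and correctly fails in all three rows. So the passes in that table are not general. The invariance is, and a verdict that turns on spread is the problem.

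The trial-level rates set the other lesion type exactly equivalent and would be lower if it were less likely to pass.

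Keeping the original scale costs power. At a true ratio of 1.0, 50% reduction, log-SD 0.8 and 200 per arm, original-scale Fieller passes about 50% against 97% on the rank path; at 500 per arm it passes 94%. But in that 200-per-arm cell the rank path also passes about 47% of products whose true ratio is 0.80.

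**Conclusion.** The concern holds. Followed as written, the skewed-data branch turns the equivalence decision into one about p between 0.389 and 0.611, and it does not control the 5% error at a true ratio of 0.80. The first part is algebra for equal arms and needs no redacted figure.

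The size is conditional. Error is badly inflated when the SD is large relative to the mean reduction, near nominal when the trigger is rare, and well below 5% where the rank rule is too strict. The claim is loss of control, not inflation in every case. All rates rest on assumed distributions, means, SDs and sample sizes, and the chance that the trigger fires is unknown. Because this branch can decide the primary conclusion, it should be corrected before unblinding.

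The rank ANOVA for superiority is a test of no difference and does not have this margin problem.

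**What to change.** In SAP 7.6.2.1 and Appendix 11.2:

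- Do not apply Fieller or [0.80, 1.25] to ranks.
- When skewness is outside ±2, keep the ratio of mean percent change as the estimand. Take its 90% interval from a nonparametric bootstrap stratified by treatment and centre, and compare that with [0.80, 1.25]. This meets Protocol 10.3.3.2.
- Fix in advance the bootstrap type, the number of resamples (the checks above used 300 to 500), the seed, whether the ratio uses raw or LS means, and how small treatment-by-centre cells are handled after the pooling in 7.6.1.
- Make the switch binding, and align section 5, 7.6.2.1 and Appendix 11.2.
- Ranks may stay for superiority. Run the skewness check and the ranking separately by lesion type, name percent change in the rank code (it now ranks change from baseline), and state the rule for both lesion types, since 7.6.2.1 names only inflammatory counts.

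The cost is SAP wording and a short program before unblinding. It needs no new data, no extra patients and no protocol change. Power with wide spreads will be lower than the rank path appears to offer, and should be checked against the sponsor's unredacted assumptions.
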